naturalistic drinking contexts to assess the strength of the association between a novel TAC sensor (BACtrack Skyn) and breath alcohol (BrAC) measurements. In addition, we will also use a small non-intrusive light-based blood flow measurement device (placed on the participant's finger) and validate these measurements against the other metrics. These aims will be accomplished using data from two half-day visits to our lab at UNC campus, 1-2 days apart, followed by a 7-day remote assessment study and a final brief discharge visit (Figure 1). Lab visits involve a novel self-report questionnaire to assess alcohol-specific satiety during a paced alcohol challenge paradigm. In addition, on each of the two sessions in counterbalanced order, participants receive either a dietary supplement intended to stimulate postprandial GLP-1, or a calorically matched placebo to assess the effect of GLP-1 stimulation on alcohol-specific satiety. Two blood samples will be collected at each session to confirm plasma levels of glucagon-like peptide 1 (GLP-1). Blood fingerprick samples will be used to measure high-mobility group box 1 (HMGB1) inflammatory marker at three timepoints after alcohol administration. Additional measures of reward and incentive motivation for alcohol will be included to test the hypothesis that satiety is associated with reduced incentive motivation for alcohol reward. At the end of the second lab visit participants will be oriented to the 7-day remote assessment study. During the 7-day remote visit participants will be asked to wear the Skyn sensor continuously across 24-hours/day, except when bathing/showering or charging the device, and to initiate EMAs if they start an alcohol drinking bout. During drinking bouts, and for up to one hour following drinking bouts, participants will be prompted to record their BrAC every 20 minutes and to self-report the number of drinks consumed since the prior survey and subjective intoxication. Each morning, participants will complete daily diaries reporting alcohol-related harms experienced on the prior day. Following the 7-day remote visit, participants will complete a final discharge visit to return study devices, complete a timeline follow-back, and undergo a dual x-ray absorptiometry (DEXA) scan to assess fat-free mass, which will be included as a covariate in subsequent analyses to account for alcohol-elimination rate [56]..

[figure not shown]

Figure 1. Diagram of lab session procedures

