After the paced drinking procedure, a final fingerprick blood sample will be taken and participants will remain in the lab until their BAC reaches 0mg% at which point they will be either dismissed. At the end of the second lab session, participants will receive instructions on using the Skyn and BACtrack S80 devices, using the Skyn app for syncing Skyn data and the LifeData app for completing drinking bout EMA surveys and morning surveys about past day alcohol use and consequences.

Remote assessment

During the 7-day naturalistic study, participants will be asked to wear the Skyn for 24 hours/day for 7-days (except when bathing or swimming). On days when participants choose to drink they will initiate drinking bout surveys via smartphone by indicating they have started drinking, after which they will be prompted to provide a BrAC reading once every 20-minutes throughout the drinking bout and for up to 1-hour after the drinking bout ends. Every 60-minutes participants will also self-report alcohol amount and subjective intoxication during the drinking bout. Importantly, participants will be informed that they are not expected to change their drinking behaviors during the study and compensation is not contingent on self-reports or breathalyzer readings during drinking bouts. Participants will complete daily morning surveys about past day alcohol use and consequences and evening surveys about daily pain and stress.

After the 7-day protocol, participants will return their devices to the PI's lab and report past 7-day drinking behaviors (timeline follow-back; TLFB) and drinking consequences (Brief Young Adult Alcohol Consequences Questionnaire, Importance of Consequences of Drinking short-form) and undergo a DEXA scan. Participants will be compensated upon device return with up to \$240 (\$20 for baseline surveys, \$50 for lab visit one, \$50 for lab visit two, \$70 for all 7-day EMA study procedures, \$10 for device return, \$10 for follow-up questionnaires, \$10 for DEXA scan, and \$10 study completion bonus).

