BACtrack Skyn TAC Monitor: The BACtrack Skyn is a small, lightweight wrist monitor that measures alcohol exposure through the 1% of alcohol transmitted through perspiration (i.e., transdermal alcohol concentration). The device wirelessly syncs to the Skyn app on the participant's iPhone to collect TAC data every 20 seconds. Alcohol exposure is detected with an average delay of 35.6 minutes [84]. The following outcomes are derived from TAC data: *drinking intensity* (peak TAC and area under the curve [AUC]), *drinking duration* (hours with TAC >0 µg/L air), *rise rate* (average rate of all ascending point-to-point TAC values), and *fall rate* (average rate of all descending point-to-point TAC values).

BACtrack S80 BrAC Monitor: The BACtrack S80 is a portable, battery-operated professional breathalyzer that measures the percentage of alcohol in a person's breath (i.e., BrAC). Participants capture BrAC within seconds after following a series of automated instructions provided by the S80 and breathing into the mouthpiece. Participants will report their S80 readings in the EMA surveys. The outcomes derived from the BrAC data are the same as those described above for TAC data.

Behavioral tasks:

The alcohol purchase task (APT) measures the hypothetical behavioral economic demand for alcohol at 14 different price points. This measure is sensitive to the reinforcing effects of alcohol, and predictive of real-world alcohol consumption [69]. The following outcomes are derived from the APT: APT-intensity (consumption when drinks were free); APT-breakpoint (the first price at which consumption was suppressed to zero); and APT-Omax (maximum alcohol expenditure) [69]. The task takes no more than 5 minutes to complete and is administered on REDCap

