8. STATISTICAL CONSIDERATIONS

8.1 SUMMARIZE THE STATISTICAL ANALYSIS STRATEGY FOR EACH SPECIFIC AIM

Descriptive statistics (e.g., frequency, mean, standard deviation, variance, range) will be generated for all study variables. Continuous study variables will also be examined for normality and homogeneity of variances using visual inspection methods (e.g., histograms, box plots, residuals, Normal Q-Q plots) and quantitative methods (Shapiro-Wilk test). If these assumptions are violated, the continuous study variables will be transformed, as necessary (e.g., log transformation). Exploratory analysis of the association between participant characteristics and study outcomes will be tested using Pearson correlation coefficients, chi square, and analysis of variance.

To analyze study aims 1 and 2, multi-level regression models will examine the within-person correlations between TAC and BrAC measurements, including peak TAC/BrAC and area under the TAC/BrAC curves (AUC). Models will test within-person correlations between TAC and BrAC during the in-lab alcohol administration and naturalistic drinking bouts and will investigate whether correlations differ across conditions. Multi-level models will test TAC predicting drinks consumed and the odds and frequency of alcohol-related harms (e.g., hangover, missed classes), and will examine whether BrAC accounts for additional variance in those outcomes. Person-specific algorithms for predicting BrAC from Skyn TAC data will be developed using a backwards step-wise multiple linear regression approach starting with Skyn TAC data as the primary predictor and adding relevant covariates (e.g., fat-free mass, skin temperature) that result in statistically significant and/or clinically meaningful improvements to the model.

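### The two Skyn removal rules differ, neither keeps removal away from drinking bouts, and no TAC outcome has an off-wrist rule, so field TAC can be lost after a bout and scored in an unstated way

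*Combined protocol and SAP*

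**What the plan says.** The combined protocol and SAP gives the field wear rule twice. Section 4.1 (Overall Design) tells participants to "wear the Skyn sensor continuously across 24-hours/day, except when bathing/showering or charging the device". Section 4.3 (Remote assessment) tells them to "wear the Skyn for 24 hours/day for 7-days (except when bathing or swimming". Charging appears only in the first and swimming only in the second. Neither says when removal may happen relative to a bout.

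The BACtrack Skyn paragraph of Section 4.3 says the device and app "collect TAC data every 20 seconds", and then: "Alcohol exposure is detected with an average delay of 35.6 minutes". It derives drinking intensity ("peak TAC and area under the curve [AUC"), duration ("hours with TAC >0"), rise rate, and fall rate ("average rate of all descending point-to-point TAC values"). It gives no wear criterion, no gap rule and no time window for any of them. Section 8.1 carries the measures into the Aim 1 and 2 models, "including peak TAC/BrAC and area under the TAC/BrAC curves (AUC", without a missing-data or non-wear rule. Skin temperature is named there only as a possible covariate for predicting BrAC.

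BrAC prompts in the field stop at most 1 hour after the bout. The checks in Sections 9.1.7.1 and 9.1.9.1 are general completeness and range checks and do not define wear.

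**The concern.** Aim 1 compares the TAC-BrAC correlation in the laboratory with that in the field. Aim 2 compares TAC with BrAC as predictors of drinks and harms. Laboratory wear happens in a staffed session; field wear includes permitted removals. Taking off the Skyn does not disturb a breath reading. Loss of TAC after a bout would therefore fall on one setting in Aim 1 and one measure in Aim 2, and could be mistaken for a property of the sensor.

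TAC that was never recorded cannot be recovered, so the instruction on when to charge has to be settled before data collection. How gaps are scored can move AUC a good deal, and if left open it could be decided after the data are seen.

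**Working it through.** The plan states no figure to reproduce on this point, so the check is a reading of the text followed by an illustration.

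**Inputs from the documents.** One TAC reading per 20 s (180 per hour); average delay 35.6 min = 0.593 h; BrAC prompts end at most 1 h after the bout.

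**Assumptions not in the documents.** A 2-h bout rising linearly to 65 mg% (BAC-equivalent), a decline of 15 mg% per hour, TAC as the same curve shifted by 0.593 h, and off-wrist readings recorded as zero and kept.

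**How much of the curve follows the bout.**
- Total duration: 2 + 65/15 = 6.33 h. True AUC: 0.5 × 65 × 6.33 = 205.8.
- When drinking stops, TAC has run for 2 − 0.593 = 1.407 h and stands at 65 × 1.407/2 = 45.7. Area so far: 0.5 × 1.407 × 45.7 = 32.2, or 16% of the total. The other 84% lies after the bout.
- For a 4-h bout to 100 mg% (AUC 533.3), the area by the end of drinking is 0.5 × 3.407 × 85.2 = 145.1, or 27%, which leaves 73%.

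**Off for 1 h, starting 1 h after the 2-h bout.**
- TAC at removal: 65 − 15 × 0.407 = 58.9. At return: 58.9 − 15 = 43.9. Area lost: 51.4, so 51.4/205.8 = 25% of AUC.
- Duration kept: 5.33/6.33 = 84%.
- Peak is unchanged, because the TAC peak came 35.6 min after the bout.
- Fall rate: 600 true descending steps at 15 per hour plus one false step of 58.9 × 180 = 10,602 per hour. The mean is (9,000 + 10,602)/601 = 32.6, about 2.2 times true.
- Rise rate: 360 steps at 32.5 plus one of 43.9 × 180 = 7,902. The mean is (11,700 + 7,902)/361 = 54.3, about 1.7 times true.

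**Off from 1 h after the bout for the rest of the curve.** Area lost: 58.9²/(2 × 15) = 115.6, or 56% of AUC.

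**Gap over the peak (off from 0.25 to 1.25 h after the bout).** The highest reading left is 65 − 15 × 0.657 = 55.1, or 85% of the true peak.

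**Range over bouts of 2 h to 65 mg% or 4 h to 100 mg%, declines of 12-20 mg% per hour, and gaps of 20 min to 2 h.** Scored as zero, AUC is 57-96% of true, duration 62-97%, rise rate 1.0-2.2 times and fall rate 1.3-3.3 times true. The same gaps bridged by linear interpolation give AUC of 96-101% and duration of 100-103%, but peak stays at 83-92% when a 1-h gap covers it.

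**Second model.** Four to six drinks of 20 mg% every 30-45 min, elimination 15 mg% per hour, TAC as a first-order lag of 35.6 min, off-wrist scored as zero:

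| Removal | TAC AUC lost |
|---|---|
| 30 min, from 30 min after last drink | 10-15% |
| 1 h, from 30 min after last drink | 20-29% |
| Rest of night, from 1 h after last drink | 43-59% |

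**AUC correlation.** Simulated bouts of 2-7 drinks with log-SD 0.2 sensor noise; affected bouts lose the rest of the night from within 2 h of the last drink:

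| AUC definition | No removal | 25-50% of bouts affected |
|---|---|---|
| Full TAC and full BrAC curves | about 0.94 | 0.82-0.78 |
| BrAC ends 1 h after bout, full TAC | 0.89-0.91 | about 0.75-0.83 |
| Both end 1 h after bout | about 0.93 | about 0.91 |

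With 1-h removals in place of overnight ones, the full-curve correlation falls only to about 0.92. The peak correlation moves by at most about 0.007.

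**The case against.** The documents never say what the Skyn records off the wrist or on a charger, or how gaps will be treated. A reader might infer that removal will be scored as low exposure. The text supports only that the scoring is unspecified, and interpolating gaps of up to 2 h nearly restores AUC. This stands.

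A reader might also infer that every participant is affected. Permission to charge at some time in 7 days is not removal during a post-bout curve. Battery life, charging time and shower timing are not given, and the 25-50% share of affected bouts is assumed. This stands too.

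Peak, one of the two measures named in Section 8.1, is almost untouched. Rise and fall rates would go up, not down, and Section 8.1 does not name them for the models.

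Nor is BrAC AUC a complete yardstick in the field. With prompts ending 1 h after the bout, 26-46% of BrAC AUC goes unobserved under the second model's assumptions. With both curves cut there, overnight removal costs the correlation little. But no TAC window is stated, so that protection cannot be assumed.

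Finally, this is a pilot, and the differing lists may be loose wording between an overview and the procedures. Even so, the two lists cannot both serve as the participant instruction, and changing the instruction is nearly free.

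**Conclusion.** The concern holds in a conditional form. The two removal lists differ, neither keeps removal away from bouts, and no TAC outcome has an off-wrist rule. With a 35.6-minute average delay, permitted removal after a bout can lose field TAC.

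If off-wrist readings are near zero and kept, AUC and duration are under-read and rise and fall rates are inflated, while peak changes little unless the gap covers it. The AUC loss is 10-29% for 30-60 minutes off, and 43-59% if off from 1 h after the last drink, per affected bout and under assumed bout shapes. How many bouts would be affected is unknown.

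The documents do not support a claim that the field correlation will fall from about 0.94 to about 0.8. That needs zeros kept, full unmatched curves, and overnight removal in 25-50% of bouts. With matched windows the fall is about 0.02. The change is worth making because it is cheap and the lost data cannot be recovered.

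**What to change.** 1. State one wear rule, identical in Sections 4.1 and 4.3. Tell participants to charge at a set time away from drinking, for example after the morning survey, and not during a bout or the night after it.
2. In Sections 4.3 and 8.1, set off-wrist TAC to missing, not zero, before deriving any outcome. Identify it from skin temperature if the device records that continuously (the documents do not say), otherwise from a participant removal and charging log. Bridge short gaps by interpolation, with the limit fixed in advance. Exclude from AUC and duration any bout with a long gap, and from peak any bout whose gap covers the expected TAC peak.
3. For the Aim 1 AUC correlation, compute TAC and BrAC AUC over a matched window, since BrAC prompts stop at most 1 h after the bout. Add a sensitivity analysis on fully worn bouts.

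The cost is one more participant instruction, a short derivation rule, and a few bouts dropped from some analyses.

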4.2 PARTICIPANTS

We will aim to recruit 42 adults who meet NIAAA criteria for at-risk drinking; >7/14 standard drinks per week for women/men, with at least one past-month heavy drinking episode defined as 4/5+ standard drinks for women/men. To ensure a range of alcohol use in the sample we will aim to recruit an even number of participants from AUDIT zones 1, 2 and 3 (AUDIT total score = 0-7, 8-15, and 16-19 respectively) which reflect different levels of alcohol use health risk severity [57]. The AUDIT is a validated screening tool that indexes alcohol use severity, but is not a diagnostic instrument. Typically an AUDIT score of 20 or greater indexes elevated risk for alcohol use disorder; those with scores of 20+ will be excluded. In addition, we will aim to recruit an even distribution of males and females across AUDIT zones. Participants will be recruited via flyers and social media ads from the triangle area (Chapel Hill, Raleigh, Durham). Interested participants will fill out an online pre-screen survey using Research Electronic Data Capture (REDCap) to determine initial eligibility. We estimate screening 250 people will yield 55 eligible participants to consent. Accounting for study drop-outs, we expect that 55 consents will allow for a final sample size of 42 who complete all study procedures, which is a feasible goal for the 12-month study. Potentially eligible participants will be contacted via email to schedule a virtual visit including additional screening and informed consent. A research assistant will explain the study requirements and both parties will sign the consent documents via REDCap if agreeing to enroll in the study. The DSM-5 SCID will then be administered to screen for alcohol and substance use disorder.

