1.2 SCHEDULE OF ACTIVITIES (SOA)

Procedures	Online Prescreen	Virtual Visit	Study visit 1	Study Visit 2	7 day Remote Assessment	Discharge visit
Online prescreen survey	X					
Informed consent		X				
DSM-5 SCID AUD and SUD		X				
Demographics Form		X				
Alcohol Use Identification Test (AUDIT)		X				
Inventory of Drinking Situations (IDS)		X				
Obsessive Compulsive Drinking Scale (OCDS)		X				
Reward-based Eating Drive Scale (RBEDS)		X				
Body Perception Questionnaire (BPQ)		X				
Drinking Motives Questionnaire (DMQ)		X				
Comprehensive Relative Autonomy Index for Drinking (CRAI Drinking)		X				
Alcohol Sensitivity Questionnaire (ASQ)		X				
Impaired Control Scale (ICS)		X				
Dietary supplement or placebo			X	X		
Administer alcohol priming drink			X	X		
Paced alcohol or control drinking			X	X		
Weight and height			X			
Pregnancy test			X	X		
Alcohol-specific satiety questionnaire			X	X		
Drug Effects Questionnaire (DEQ)			X	X	X	
Visual Analogue Scale (VAS)			X	X		
Biphasic Alcohol Effects Scale (BAES)			X	X		
Subjective Effects of Alcohol Scale (SEAS)			X	X		
Alcohol Urge Questionnaire (AUQ)			X	X		
Alcohol Purchase Task (APT)			X	X		
Dot Probe task			X	X		
Breath Alcohol Concentration (BrAC)			X	X	X	
Transdermal Alcohol Concentration (TAC), measured via Skyn			X	X	X	
Ecological Momentary Assessment (EMA)					X	
DEXA scan					X	
Venipuncture blood sample x2			X	X		
Fingerprick blood sample x3			X	X		
Timeline followback (TLFB)						X
Brief young adult alcohol consequences questionnaire						X
Importance of consequences of drinking short-form						X
Return Skyn monitor						X

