5.2 EXCLUSION CRITERIA

An individual who meets any of the following criteria will be excluded from participation in this study.

- Meets past-year criteria for severe AUD (>7 of 11 symptoms endorsed) or AUDIT score of 20+
- Meeting past-year criteria for a substance use disorder (with the exception of alcohol, tobacco or mild cannabis use disorder)
- Current engagement in alcohol treatments, or currently engaged in intentional efforts to quit alcohol use
- Current use of GLP-1 receptor agonist medication or weight control medications
- Lifetime diagnosis of severe mental illness (including schizophrenia and bipolar disorder)
- History of suicide attempt, or recent (past 30 day) suicidal ideation, or psychiatric hospitalization in the last 6 months
- History of diabetes
- Medical conditions or medications for which alcohol is contraindicated

- Pregnant, nursing, or trying to become pregnant
- Plans to travel during the duration of study participation

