To analyze study aim 3, multi-level regression models will be used to assess within-person changes on repeated measures along with between-person individual differences. A linear growth curve model will be used to test the hypothesis that alcohol-specific satiety increases with time and additional drinks. Timepoint (1-6) and drug (alcohol or placebo) will be included in the model as within subject factors. Compared to placebo, alcohol is predicted to be associated with higher rates of change (slope) in satiety. Next, AUDIT will be included as a continuous predictor of slope in the model to test the hypothesis that participants with fewer alcohol dependence symptoms (lower AUDIT scores) report reduced satiety. Finally, subjective craving scores (Alcohol Urge Questionnaire; AUQ) from each timepoint will be included in the model. The effect of satiety over time is expected to remain significant after controlling for craving. Alcohol-specific satiety is expected to be negatively associated with measures of reward and incentive motivation for alcohol (BAES, APT, Dot Probe). Outcomes from each of these measures will be included in separate multi-level models with satiety scores as the primary dependent measure and timepoint (1-6) and drug (alcohol, placebo) as within-subject factors to determine the effect of additional dependent measures on within-person change in alcohol specific-satiety over time (slope).

To analyze aim 4, a repeated measures analysis of variance (ANOVA) will be used to assess the effect of a dietary supplement on alcohol-specific satiety in a 2(alcohol, placebo) x 2(timepoints) design. It is

predicted that compared to placebo, a GLP-1 stimulating dietary supplement will increase alcohol-specific satiety.

To analyze aim 5, linear regression will be used to assess the association between HMGB1 levels as a function of BrAC during the laboratory alcohol sessions. Data processing and analyses will be completed in R and SPSS.

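### Aim 3 words its individual-difference hypothesis as dependence symptoms but tests it only with the AUDIT, so the result should be reported as use severity and a SCID symptom-count model added

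*Combined protocol and SAP*

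**What the plan says.** **The hypothesis and its predictor.** In section 8.1 (Aim 3), "AUDIT will be included as a continuous predictor of slope in the model to test the hypothesis that participants with fewer alcohol dependence symptoms" have less satiety. The equation of the two is in the sentence itself: "participants with fewer alcohol dependence symptoms (lower AUDIT scores) report reduced satiety". AUDIT is the only baseline between-person characteristic that section 8.1 names as a predictor of satiety slope.

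**What the AUDIT is said to measure.** Section 4.2 (Participants) states: "The AUDIT is a validated screening tool that indexes alcohol use severity, but is not a diagnostic instrument". Recruitment is spread evenly over AUDIT zones 1 to 3 (scores 0 to 19) to obtain a range of alcohol use. The section ties the score to alcohol use disorder only at the top: "Typically an AUDIT score of 20 or greater indexes elevated risk for alcohol use disorder; those with scores of 20+ will be excluded".

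**What else is measured.** The schedule of activities (section 1.2) has "DSM-5 SCID AUD and SUD" at the virtual visit. Section 4.2 gives the purpose: "The DSM-5 SCID will then be administered to screen for alcohol and substance use disorder". Section 5.2 applies a symptom threshold: "Meets past-year criteria for severe AUD (>7 of 11 symptoms endorsed) or AUDIT score of 20" or above. Section 2.3.1 also screens out severe AUD but defines it as 6 or more of 11 symptoms.

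**Where the SCID does not appear.** It is absent from the list of measures that closes section 4.3, from the baseline measures which that section sets aside for exploring moderators, and from every analysis named in section 8.1.

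**The concern.** Aim 3 is about individual differences in alcohol-specific satiety, and the AUDIT term is its main test of them. The hypothesis names one construct, dependence symptoms. The predictor is, on the protocol's own description, an index of another, use severity. The two are related but are not the same thing.

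If the AUDIT coefficient is significant, the present wording invites a conclusion about symptoms even though the association could come from how heavily people drink. If it is not significant, the wording invites the conclusion that symptoms do not matter, although symptoms were never modelled. The introduction (section 2.2) links resistance to satiety with binge-like drinking as a symptom of the disorder, so the difference between drinking level and symptoms matters to what the study can claim.

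**Working it through.** **Step 1: set the passages side by side.**

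| Item | AUDIT total | SCID AUD symptoms |
|---|---|---|
| Described as | index of use severity (4.2) | criteria endorsed out of 11 (2.3.1, 5.2) |
| Stated use | recruitment zones, exclusion, Aim 3 predictor | screening and exclusion |
| Range left in the sample | 0 to 19 (20+ excluded) | 0 to 5 under 2.3.1 (6 or more excluded), or 0 to 7 under 5.2 (more than 7 excluded) |
| Named in 8.1 | yes | no |

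The construct in the hypothesis matches the right-hand column more closely, and the analysis uses the left-hand one. Both scores are truncated at the top by eligibility.

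**Step 2: the plan's own sample-size figure.** Section 8.2 gives N = 42 for 86% power, a medium effect and α = .05, for a within-between interaction. It does not state the number of groups k, the number of measurements m or the correlation ρ. Assume f = 0.25 for medium, and use λ = f²Nm/(1 − ρ) with df (k − 1)(m − 1) and (N − k)(m − 1). One combination that fits is k = 2, m = 4, ρ = 0.2: λ = 0.0625 × 42 × 4 / 0.8 = 13.1, power 0.862. Others also come close (k = 3, m = 6, ρ = 0.2 gives 0.866). So N = 42 is plausible but cannot be reproduced uniquely. The point here does not depend on it, and only N = 42 is carried forward.

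**Step 3: what using a proxy could cost (illustration).** Assumptions, none from the documents:
- symptom count correlates 0.40 with satiety slope;
- AUDIT is related to slope only through symptoms, with AUDIT-symptom correlation q;
- the symptom count is free of error and not truncated;
- the test is two-sided at 0.05.

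The expected AUDIT-slope correlation is r = 0.40 × q. By the Fisher z approximation, power = Φ(atanh(r) × √(42 − 3) − 1.96), with √39 = 6.245.

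| Predictor | r | atanh(r) × 6.245 − 1.96 | Power |
|---|---|---|---|
| Symptom count | 0.40 | 0.69 | 75% |
| AUDIT, q = 0.9 | 0.36 | 0.39 | 65% |
| AUDIT, q = 0.7 | 0.28 | −0.16 | 44% |
| AUDIT, q = 0.5 | 0.20 | −0.69 | 24% |

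**Step 4: allow for truncation of the symptom count.** Suppose 0.40 is the unrestricted correlation and exclusion cuts the count's SD to 0.7 of its original value (assumed). Then r = 0.40 × 0.7 / √(1 − 0.16 + 0.16 × 0.49) = 0.28 / 0.958 = 0.29, and power is about 47%. That is close to the 44% for AUDIT at q = 0.7, so the 75% is a best case for the symptom count.

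**Step 5: the reverse case.** If slope depends only on consumption (r = 0.40, assumed) and AUDIT tracks consumption at 0.7, the AUDIT-slope correlation is again 0.28. AUDIT is then significant in about 44% of trials with no symptom effect. That would be a real association with AUDIT severity. Only a symptom label on it would be wrong.

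**The case against.** Several objections have force.

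- **Not being diagnostic is no defect here.** A reader might infer that the AUDIT is unfit for Aim 3 because the protocol calls it non-diagnostic. Aim 3 diagnoses nobody, and a continuous moderator need not be diagnostic. The mismatch is use severity against dependence symptoms, and nothing more.
- **The operationalisation is open.** A reader might infer that the planned model does not test the stated hypothesis. Section 8.1 says in the same sentence that fewer symptoms means lower AUDIT scores, so anyone can see what was measured. The model remains valid for AUDIT severity.
- **AUDIT is a coherent choice.** Recruitment is designed to spread AUDIT scores and balance sex across zones. Nothing does that for the symptom count, and this is a pilot study. This is a good reason to keep the AUDIT model.
- **The alternative is less secure than it looks.** That a count exists follows from the exclusion threshold, but no section says it is kept as analysis data. A reader might also infer that the SCID is certainly never analysed. The general exploratory analysis of participant characteristics in section 8.1 could include it, though it does not name it.
- **Labels.** The hypothesis says dependence and the SCID assesses DSM-5 alcohol use disorder, so the match is closer but not literal.

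What stands after these is that no named analysis addresses symptoms directly, and that the current wording would attach a symptom conclusion to a severity score.

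**Conclusion.** The point holds as a matter of labelling and of a missing model, not as a flaw that invalidates Aim 3. The AUDIT analysis supports a statement about use severity. On the protocol's own description of the instrument, it does not support one about dependence symptoms in either direction.

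The documents do not allow the size to be fixed. The loss from using AUDIT as a proxy runs from modest (75% to 65%) to large (75% to 24%) across the assumed correlations, and plausible truncation of the symptom count could remove most of the gap. A reader should not take these figures as a demonstrated loss of power, or as proof that the symptom count is the better predictor. The case for change is that it lets Aim 3 answer the question it asks, at little cost.

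**What to change.** In section 8.1, Aim 3:

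1. Keep AUDIT as the continuous predictor of satiety slope, and word its hypothesis and conclusion as alcohol use severity.
2. Add one pre-specified model with the SCID AUD symptom count as the continuous predictor of slope, for the dependence-symptom hypothesis. Report both models whatever they show.
3. Add the SCID symptom count to the list of measures in section 4.3 and state that it is retained as analysis data.
4. Reconcile the severe-AUD cut-offs in section 2.3.1 (6 or more of 11) and section 5.2 (more than 7 of 11), because they determine the range of the count.

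The cost is some wording and one model on an assessment the eligibility screen already requires, with no new visits or participants. The downsides are one more test to report and a symptom count cut short by exclusion, although AUDIT is cut short too. The change should be made before the data are analysed, because choosing between the two measures afterwards would look data-driven.
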